**Detailed protocol**

**Drugs Brain and Behavior (DA02812)**

**PI [name], Co-I's [name], [name]**

**NCT #: NCT04642820**

**Nov 9, 2020**

### **Specific Aims.**

Addiction, especially addiction to stimulant drugs, remains an urgent public health problem. In 2016-7 as many as 5 million Americans reported misusing prescription stimulants, and 0.4 million had stimulant use disorders. In a recent survey of 5,585 young women aged 10-18, 6.6% reported nonmedical use of stimulants. Of all the people who try stimulant drugs, only a subset go on to develop dependence. The risk factors for escalating use are poorly understood. One biologically plausible, but understudied, source of risk for repeated use of drugs is individual variation in brain reward circuitry. Stimulant drugs have primary actions on the dopaminergic mesolimbic reward system, which also mediates sensitivity to other rewards. Individuals vary in their subjective and behavioral responses to stimulants and these variations may be related to brain reward function. We recently found that individuals who exhibited *greater* striatal brain activity during anticipation of a monetary reward experienced greater euphoria and drug liking after a single dose of amphetamine (determined on a separate session). Studying effects of drugs on brain reward circuits in relation to behavioral indices of reward offers a promising new avenue for identifying a biological basis for risk for stimulant drug use.

In this project, we will examine individual differences in the effects of a stimulant drug, methamphetamine (MA), on mesolimbic reward function using fMRI. We will determine how individual differences in neural activity after the drug are related to its behavioral, rewarding effects. The effects of MA on mesolimbic reward function will be examined using both reward-task-related activation and resting state functional connectivity. On separate sessions, we will examine the effects of MA on behavioral reward in the same subjects, using ratings of drug liking and euphoria, as well as measures of drug seeking (drug and dose choice). Our goal is to identify neural processes that predict MA liking and 'seeking' behaviors. We have preliminary evidence that amphetamine increases striatal brain activity during a nondrug reward task, and that it facilitates frontal-striatal resting state functional connectivity. We will extend these observations to a larger sample using a more sensitive task, more refined imaging techniques, more comprehensive behavioral assessment and sufficient power to compare men and women. Healthy young adults will first undergo two fMRI scans with placebo and MA (20 mg), while performing the Monetary Incentive Delay and the Doors task. Then, they will participate in two behavioral sessions conducted in our laboratory. We will examine correlations between the neural responses and behavioral responses to MA.

**Specific Aim 1. To determine the effects of MA on regional brain activity during anticipation of reward, task-related functional connectivity and resting state connectivity.** We will examine the direct effects of a moderate dose of MA (20 mg) vs placebo on mesolimbic circuits. Imaging measures will include on regional activation during two reward tasks, task-related changes in functional connectivity, and resting state functional connectivity. These measures of assess different dimensions of brain function impacting reward processing. We hypothesize that MA will increase activation in striatal regions during anticipation of reward, and enhance both task-related and resting state functional connectivity in fronto-striatal reward circuits. We also expect that there will be inter-subject variability in these effects.

[figure not shown]
**Specific Aim 2. To examine the relationship between neural effects of MA and behavioral rewarding effects of MA.** We will examine the relationship between the neural effects of MA (task-related and resting state) and rewarding behavioral responses to the drug. Neural effects will be assessed as in Aim 1. Behavioral responses to MA will be assessed in a 2-session procedure providing drug liking ratings as well as measures of reward learning. We hypothesize that greater magnitude of effects of MA on brain reward function (regional activation and connectivity) will be related to greater behavioral rewarding effects. Specifically, we hypothesize that MA-induced increase in fronto-striatal resting state connectivity will be linked more strongly to tonic increases in drug liking, whereas task-related striatal activation will be associated with greater reward learning on the learning task.

The project will advance our understanding of how stimulants alter neural reward processes, and how individual differences in brain function predict variation in the rewarding and cognitive effects of drugs. The findings will help to develop novel treatment approaches, including medications or noninvasive

techniques such as transcranial magnetic stimulation, that target reward substrates in addicted individuals.

### **Background.**

This project will investigate the effects of methamphetamine (MA) on brain reward circuits in relation to its effects on behavioral indices of reward. Healthy volunteers will first engage in two fMRI imaging sessions in which they will receive MA (20 mg oral) or placebo (PL) under double-blind conditions. These scanning sessions will assess i) regional activation and connectivity in mesolimbic circuits during anticipation and receipt of reward, and ii) resting state functional connectivity in fronto-striatal circuits. Then, during two behavioral sessions, subjects will receive MA or PL during two sampling sessions on which they will complete mood and drug liking questionnaires and complete simple learning tasks.

### **Methods.**

We address the following questions: i) does MA alter either regional activation or task-related connectivity in mesolimbic regions during anticipation of reward, ii) does MA alter resting state functional connectivity in mesolimbic and frontostriatal circuits, iii) are the neural effects of MA on reward circuitry (task-related or resting state connectivity) related to the rewarding effects of the drug, as measured by drug liking, or to its effects on simple learning? We will utilize several indices of drug reward: ratings of drug liking or euphoria. We have shown that ratings of drug liking are highly related to measures of drug seeking. We will also examine sex differences, and control for menstrual cycle phase in women (White, Justice et al. 2002).

MA is a prototypic stimulant drug with a well-defined mechanism of action. We have conducted many studies with MA at the doses proposed here, and its effects on mood and cardiovascular function are robust and reliable (Wachtel, Ortengren et al. 2002; Soderpalm, Nikolayev et al. 2003; Mayo, Fraser et al. 2013; Ballard, Weafer et al. 2015; Bershad, Kirkpatrick et al. 2015). MA produces effects that are very similar to d-amphetamine (Childs and de Wit 2013; Weafer and de Wit 2013; Hart, Gamazon et al. 2014; Wardle, Marcus et al. 2015; Childs, Bershad et al. 2016). Both drugs increase synaptic levels of dopamine and norepinephrine, and to a lesser extent serotonin (Moore 1977) by releasing neurotransmitter from the vesicles in the pre-synaptic neuron, as well as blocking re-uptake and inhibiting degradation by monoamine oxidase. We selected MA because it has a slightly faster onset of effects. There is evidence that the rewarding effects of amphetamines are mediated by its actions on dopamine, with some role also for norepinephrine (Laruelle, Abi-Dargham et al. 1995; Kumari, Corr et al. 1997; Mattay, Callicott et al. 2000; Drevets, Gautier et al. 2001; Navarra, Clark et al. 2017).

Participants will be healthy young men and women (N=80, 80). They will first participate two fMRI scans, when they receive oral MA (20 mg) and PL, in random order under double blind conditions. During the scan they will complete the Monetary Incentive Delay task (MID) (Knutson, Adams et al. 2001) and the Doors task (Carlson et al. 2011) and resting state data will be obtained. The primary outcome measures during these sessions will be task-related (anticipation and receipt of reward) regional brain activation, task-related connectivity, and resting state functional connectivity. After the two scans, subjects will participate in two behavioral sessions during which they receive MA (20 mg oral) or PL in mixed order, in color-coded capsules. Subjects will complete mood and drug effects questionnaires, and cognitive tasks.

**Subjects.** Healthy men and women aged 18-35 years will be recruited from the university and surrounding community without regard to race or ethnicity, according to Protocol 13681B. Initial

eligibility will be ascertained in a telephone interview (age, current drug use, medical conditions), and appropriate candidates scheduled for an in-person interview with a physical examination, EKG and a structured clinical psychiatric interview (First, Williams et al.). Their screening information will be approved by a physician. Subjects must have a high school education, fluency in English, body mass index between 19 and 26, and good physical and mental health. Exclusion criteria are serious psychiatric disorder including psychosis, severe PTSD or depression, any regular prescription medication, contraindications for fMRI scanning, history of cardiac disease, high blood pressure, consuming >4 alcoholic or caffeinated beverages a day, or working night shifts. Subjects will be excluded either if they report never having used any substance for nonmedical purposes, or if they have experienced adverse responses to any of the drugs they might receive. This information is obtained during in-person screening by a trained clinical interviewer. Women who are not on oral contraceptives will be tested only during the follicular phase (1-12 days from menstruation) because responses to stimulant drugs are dampened during the luteal phase of the cycle (White, Justice et al. 2002). We recognize that the 5 sessions will need to be scheduled across two months for women not on oral contraceptives. Before participating subjects will complete several questionnaires: a psychiatric symptom checklist, the BIS/BAS, the Depression, Anxiety and Stress Scale (DASS) (Lovibond and Lovibond 1995) and the Multidimensional Personality Questionnaire (Patrick, Curtin et al. 2002).

**Consent.** Qualifying subjects will attend an orientation session to familiarize them with the methods and obtain informed consent. Subjects will be told that the purpose of the study is to investigate the effects of psychoactive drugs on mood, brain and behavior. To reduce expectancies, they will be told that they might receive a placebo, stimulant/anorectic, opioid, alcohol or sedative/tranquilizer. They agree not to use any drugs except for their normal amounts of caffeine for 24 hours before and 6 hours following each session. Subjects are informed that drug testing will occur before each session. Pregnancy and drug tests are conducted before each session using urine drug tests (ToxCup, Branan Medical Corporation) and breathalyzer tests (Alcosensor III, Intoximeters), and pregnancy tests (AimStickPBD, hCG professional, Craig Medical Distribution). Positive tests lead to rescheduling or dismissal from the study.

**Testing environments.** Screening and behavioral testing will be conducted individually in comfortably furnished rooms with a couch, easy chair, side table, coffee table, television and video player. Subjects may relax, read or watch neutral movies when they are not completing study measures. Scanning will be conducted in the Magnetic Resonance Imaging Research Center (MRIRC) located a 3-min walk from the behavioral testing rooms.

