#### *Procedures*

Session	Orientation	Scan 1	Scan 2	Behav Session 1	Behav Session 2
Drug	Practice	MA*	PL*	PL*	MA*
Measures	MID Doors	Self-report Mood drug, cv	Self-report mood drug, cv	Self-report Mood drug, cv	Self-report mood drug, cv
	EEfRT	fMRI with MID, Doors and motor	fMRI with MID, Doors and motor	EEfRT	EEfRT
	Stop Task			Stop Task	Stop Task
	Simple reaction time			Simple reaction time	Simple reaction time
	Go-No-Go			Go-No-Go	Go-No-Go
	Continuous performance task gradCPT			Continuous performance task gradCPT	Continuous performance task gradCPT
	Weather Prediction Task			Weather Prediction Task	Weather Prediction Task
	Learning task			Learning task	Learning task

PL=placebo, MA=methamphetamine, \*orders counterbalanced

**(i) Imaging (2).** The two fMRI sessions will assess brain activity under the influence of MA and PL. After drug and pregnancy tests, we obtain baseline measures of mood, heart rate and blood pressure. At 9:15 am subjects ingest a capsule (PL or MA 20 mg) under double-blind conditions. The scan will be conducted from 60-120 min after ingestion of the capsule at the time of peak drug effect. During the scan subjects will complete the MID and the Doors task and have a resting state scan. We will obtain several indices of the effects of MA on reward circuit function: i) for reward anticipation: regional brain activation during the MID, MID task-related functional connectivity, ii) for reward receipt, regional brain activation during the Doors task, Doors task-related functional connectivity and iii) resting state functional connectivity. Subjects will also complete one other task assessing motor reactivity.

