**Imaging data analysis.** Imaging data from fMRI tasks will be preprocessed and analyzed using AFNI tools, as in Van Hedger (Van Hedger, Keedy et al. 2018). Preprocessing steps include alignment of each time series, spatial registration of the aligned time series to the anatomical scan, anatomical scan warped to standard space and warp applied to functional data, functional data spatially smoothed, and intensity normalization. Neural activation for conditions of interest from each task will be estimated using AFNI's 3dDeconvolve program, incorporating motion and heart rate/respiration as regressors. For MID, we will use a gamma response function to create activation maps for each task element: cues, motor response, and feedback. For the secondary tasks, we will use block functions and create contrast maps between the two block types. Mean activation for each subject at each scan session will be extracted from regions of interest (ROI). For MID, ROIs will be 8mm spheres created around coordinates reported in a recent meta-analysis of 50 MID fMRI studies (Oldham, Murawski et al. 2018). For Cue: caudate, putamen ventral striatum, thalamus, and anterior insula; Feedback: ventromedial prefrontal, orbitofrontal cortex, ventral striatum, amygdala, and will be a subtraction of mean activation of loss trials from win trials in each ROI (this contrast is the most common and more sensitive approach, per Oldham); Motor: all prior ROIs (to confirm lack of drug effect), primary sensorimotor cortex. ROI activation will be a subtraction of mean activation of loss trials from win trials in each ROI (this contrast is the most common and more sensitive approach, per Oldham). We will also look specifically at win vs neutral and loss vs neutral to confirm whether findings are driven by sensitivity to reward or avoiding loss. Tapping: primary motor cortex: dorsal striatum (caudate, putamen). For connectivity analyses of the MID task and of resting state, we will use the CONN toolbox (Whitfield-Gabrieli and Nieto-Castanon 2012) which employs similar preprocessing steps (alignment and spatial standardization, intensity normalization, motion estimation, white matter and CSF-based regressors) implemented through SPM12. We will use a 2mm displacement cutoff. For MID task-related connectivity, we will conduct an ROI-to-ROI analysis, using the spherical masks described previously. The toolbox allows comparison of correlation strengths (Pearson r converted to Fisher z) of the timeseries between each pairing of the ROIs. We will compare these correlations between drug and placebo sessions, as well as extract ROI-to-ROI correlation values for assessment in relation to behavioral measures. For resting state, we will calculate seed-based connectivity maps separately for MA and placebo, as per our prior study (Weafer, Van Hedger et al. 2019). Seeds will be bilateral caudate, putamen, and ventral striatum. We will conduct paired t tests within CONN to compare connectivity following MA and placebo. As our hypotheses are specific to frontal and subcortical reward circuitry, statistical inferences will be made within an anatomically-focused frontal-insular-striatal partial brain mask. The mask will include medial and lateral frontal and orbital regions, bilateral precentral gyri, anterior and middle cingulate cortex, anterior insula and ventral striatum. Drug order will be included as a covariate in all analyses.

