Aim 2 is to determine the relationships between MA-induced changes in cortico-striatal function and positive behavioral effects of the drug (liking, and task performance). We hypothesize that MA-induced frontal-striatal activation and connectivity in reward circuits will be positively associated with behavioral measures of reward, including ratings of drug liking and attentional bias to cues. For the behavioral measures, we will first examine the degree of concordance among the different measures of MA reward (liking and attentional bias). We expect that these measures will be moderately correlated, but we also believe they measure separate components of drug reward. We will then create summary scores of drug effects (MA minus placebo) for each of the ROI's implicated in drug reward. For MID task activation, we will subtract activation during Win – Loss following placebo from activation following MA within each ROI that showed a significant drug effect. For MID task connectivity, we will subtract connectivity estimates following placebo from those following MA for each significant ROI-to-ROI connectivity pathway. For resting state connectivity, we will extract connectivity estimates from 10mm regions surrounding significant peaks for each seed, and again subtract placebo estimates from MA. These neural drug effect scores will then be analyzed in relation to each of the behavioral measures. The hypotheses are based on preliminary data (Weafer, Van Hedger et al. 2019).

a. For drug liking, we will perform linear mixed effects models for repeated measures (Hedeker and Gibbons, 2006) within SPSS25 to test the degree to which neural drug effects interact with drug and time to predict subjective measures of drug liking, measured during the behavioral phase of the study. The models will include random intercept, drug and time effects to allow for individual differences in subjective drug response and time trends, and to account for the correlation between repeated measurements. Drug order, age, and sex will be included as model covariates. The effects of interest are the two- and three-way interactions among neural drug effects, behavioral drug effects (MA vs. placebo) and time (linear and quadratic trends) on subjective liking. We hypothesize that drug liking will be correlated with NAcc-OFC connectivity.

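### Aim 2 joins two MA/PL orders whose joint assignment is not stated, and one undefined drug-order main effect leaves session-order effects in the brain–liking association

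*Combined protocol and SAP*

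**What the plan says.** The Methods section describes 160 participants ("Participants will be healthy young men and women (N=80, 80") and two MA/PL pairs. The first is "two fMRI scans, when they receive oral MA (20 mg) and PL, in random order under double blind conditions". For the second, "subjects will participate in two behavioral sessions during which they receive MA (20 mg oral) or PL in mixed order". The footnote to the Procedures table, attached to all four drug sessions, reads "orders counterbalanced". No section says how a participant's behavioral order is assigned in relation to the scan order.

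On analysis, the imaging data analysis paragraph ends "Drug order will be included as a covariate in all analyses", and Aim 1 of the Statistical Plan (C6) repeats drug order as a covariate. For Aim 2, C6 says "We will then create summary scores of drug effects (MA minus placebo) for each of the ROI's implicated in drug reward" and describes subtraction only, with no order adjustment. The liking model in item a tests how these neural scores interact with drug and time, and states "Drug order, age, and sex will be included as model covariates". It does not say which order is meant, and it lists no order-by-drug term.

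**The concern.** In a two-session crossover, an MA-minus-PL difference carries the difference between the first and second session: with a plus sign for those who had MA first, and a minus sign for those who had it second. Aim 2 relates one such difference (neural, from the scans) to another (liking, from the laboratory). Each carries its own signed session effect unless order is removed at the level of the drug contrast.

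A main effect of order acts on a participant's average level of liking, not on the MA-versus-PL difference. It therefore does not touch the neural-by-drug coefficient, which is the quantity that Aim 2 tests. Two consequences must be kept apart. If the two orders are unrelated across people, the leftover session effects are noise and weaken the association. If the orders are linked, the session effects move together and can produce an association, or cancel a real one.

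**Working it through.** **Inputs.** From the documents: N = 160, target r = 0.22, two-sided alpha 0.05 (Power analysis for Aim 2). Assumed, because the documents give no figure: a first-minus-second session difference d of 0.2 to 0.5, in SDs of the MA-minus-PL score within an order group, with the same size and sign in both phases.

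**1. The plan's own figure.** By Fisher z, power = Φ(atanh(r)·√(N−3) − 1.96) = Φ(0.2237 × 12.53 − 1.96) = Φ(0.84) = 80.0%. The stated power of over 80% reproduces (80.9% by noncentral t).

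**2. Model for order.** Let s1 and s2 be +1 for MA first and −1 for MA second in the scan and behavioral pairs, with correlation φ.

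- Neural score = true neural effect + d·s1
- Liking difference = true liking effect + d·s2
- Observed r = (ρ + d²φ)/(1 + d²), where ρ is the true correlation

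**3. Orders independent (φ = 0), true r = 0.22.** Observed r = 0.22/(1 + d²).

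| d | observed r | power |
|---|---|---|
| 0.2 | 0.22/1.04 = 0.212 | 77% |
| 0.5 | 0.22/1.25 = 0.176 | 61% |

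Type I error stays at 5%. If only behavioral order is removed at the drug-contrast level, or only scan order is, r = 0.22/√(1 + d²) = 0.216 to 0.197 and power is 78% to 71%. Both must be removed to recover the planned power.

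**4. Orders fully linked (φ = ±1).** With no true association, |r| = d²/(1 + d²). The sign is positive if the two orders match and negative if they mirror. With a true r of 0.22 and mirrored orders, observed r = (0.22 − d²)/(1 + d²).

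| d | spurious size of r, true r = 0 | rejection rate | mirrored, true r = 0.22 | rejection rate |
|---|---|---|---|---|
| 0.2 | 0.04/1.04 = 0.04 | 8% | 0.18/1.04 = 0.17 | 59% |
| 0.3 | 0.09/1.09 = 0.08 | 18% | 0.13/1.09 = 0.12 | 32% |
| 0.5 | 0.25/1.25 = 0.20 | 72% | −0.03/1.25 = −0.02 | 6% |

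**5. Does the planned covariate help?** A mixed model was fitted to one simulated data set with linked orders, d = 0.5 and no true association. The neural-by-drug coefficient was 0.188 without an order term and 0.188 with order as a main effect. Adding order-by-drug brought it to 0.028 (p = 0.60).

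**6. After the change.** With each order removed at the drug-contrast level, simulation gives type I error of about 5% and power of about 79–80% for a true r of 0.22, whether the orders are crossed, matched or mirrored. By Fisher z, two extra covariates give 79.5% against 80.0%.

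**The case against.** The best defense is that this is missing detail rather than a flaw. Counterbalancing is stated, and drug order can be read naturally as the scan order in the imaging analyses and the behavioral order in the liking model. The order effects may also be small: participants practice the tasks at orientation, are familiarized before scanning, and have MID response windows titrated between runs. The named liking hypothesis uses resting NAcc–OFC connectivity, where there is no task to practice.

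Much of this stands, and it rules out several stronger readings.

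- A reader might infer that the plan uses one order for both phases. It does not say so; it leaves the term undefined.
- A reader might take the Procedures table, with MA then PL at the scans and PL then MA in the laboratory, as evidence of mirrored assignment. It is one illustrative row. It shows that linkage is permitted, not that it is intended.
- A reader might conclude that Aim 2 faces a false-positive rate of up to 72%. That needs full linkage together with the largest assumed effect in both phases. Under mirroring the spurious r is negative, against the hypothesized positive direction, so the risk there is mainly of hiding a real association.
- A reader might think the trouble is simply two orders and one covariate. Under full linkage one order code is enough, provided it interacts with drug. Two main-effect covariates would repair nothing.

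What the defense does not answer is the form of the model. Even with drug order read as the behavioral order, a main effect leaves that order in the liking contrast, and the scan order remains in the subtracted neural score. The general sentence on covariates in the imaging paragraph does not remove it from a score formed by plain subtraction.

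**Conclusion.** The point holds in limited form. Followed as written, Aim 2 leaves session-order effects in both the neural score and the liking contrast, and the documents do not fix how the two orders relate. Aim 1 is outside the concern, because scan order is the only order there.

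The likely cost is lost power: with independent orders, from 80% to about 77–61%, with type I error intact. With fully linked orders, which are possible but undocumented, the expected r under no association is 0.04 to 0.20 in size (about 8% to 72% rejection), and mirrored orders would turn a true 0.22 into about 0.17 to −0.02. All of these sizes rest on the assumed 0.2 to 0.5 SD, equal in both phases. Smaller session effects would shrink them quickly, since they depend on d². The change is worth making because it is nearly free, not because a large bias has been shown.

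**What to change.** **Allocation.** State that behavioral order is assigned independently of scan order, using the four combinations of scan order and behavioral order balanced within sex: 160/4 = 40 per sequence, 20 men and 20 women in each.

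**Analysis.** In Aim 2, item a of C6, replace drug order with two defined terms, scan order and behavioral order, each entered with its interaction with drug. Equivalently, remove scan order from each neural score and behavioral order from the MA-minus-PL liking contrast. Where the three-way interaction with time is tested, the same reasoning calls for order-by-drug-by-time terms. If allocation has already been made and turns out to be fully linked, the two codes coincide up to sign, and one order-by-drug term serves for both.

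**Cost.** An allocation list and a revised model statement; one or two degrees of freedom, or about half a point of power; no added participants or visits. The analysis part can still be done after allocation if both orders were recorded.
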